## Exclusion criteria:

Complicated anterior segment of the eye with the following features

- 1. Deficient iris diaphragm
- 2. Aphakia
- 3. Uncontrolled Glaucoma
- 4. Age related macular degeneration causing poor visual potential
- 5. Patients unable to posture after procedure for 1-2 hours on their back
- 6. Patient's inability to position on the slit lamp interfering with post op assessments
- 7. Dementia

**Consenting** Will be done in the clinical setting at time of offering surgery. Information on the trial will be provided to patients on preoperative consultation. Patient will be given 4 weeks to decide whether he wants to take part in the trial. Should the patient decide not to take part in the trial, it will not have any impact on their clinical care.

**Randomisation:** Paper based randomisation technique will be used for enrolling the patients to either arm of the study.

An independent statistician will prepare a randomisation and concealment list by writing a script or code for a statistical package with a recorded randomisation seed to allow reproducibility. A randomisation list for each combination will be produced. This will typically be produced using blocked randomisation. As our study is blinded, a concealment list will be made to produce kit numbers in an agreed format (number of digits, prefixes and suffixes) that are linked in a random fashion to treatment. The randomisation list is then augmented with a specific kit number for each patient

A member of the team (ideally not involved) in the trial will take the randomisation list and concealment list to prepare envelopes, based on, one per patient that gives sufficient detail to assign treatment. The envelopes should be sealed with tamper-proof tape and be completely opaque. The envelopes will be enumerated in the order in which they will be opened. Ink will be used directly onto the envelope rather than pre-printed adhesive labels. A record the date/time and signature of the PI, or delegate, who opens the envelope will be made. Patients will be linked to the main body of the study data according to their hospital numbers.

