## The Primary end point is:

1. The improvement in vision measured in LogMAR units at 12 months.

The time points will be pre-operative, at 6months and then at the last visit in 12months. Our hypothesis assumes to detect a 2 line difference in final visual outcomes between the groups.

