## **STUDY PROTOCOL**

## 1St Referral clinic visit

# The following investigations and tests would be undertaken by the relevant staff of the clinical research team

Visual acuity testing performed by staff nurse /HCA

Specular Microscopy (SM) / Pentacam (Pc) / Auto-refraction (AR) / Intraocular Pressure (IOP) check / afferent pupil defect (APD) and Dilatation / Patient Quality of Life (QOL) questionnaire – **Corneal Nurse** 

Slit Lamp examination – Doctor

If suitable for enrolment, research team will be approached if doctor not part of the research study.

Study and procedure discussed – research team to include Consultant / Corneal fellow and corneal specialist nurse

Patient recruited following satisfactory consent to participate and patient listed for their anaesthetic choice LA/GA with information leaflets and 4 weeks cooling off period to make decision to participate in the trial.

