## > 4weeks post op-

- vision / IOP / specular / OCT corneal nurse
- slit lamp examination research team
- o removal of sutures
- o Patient QOL questionnaire

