## > 12 months post op

- vision / IOP / specular / pentacam / anterior segment OCT and photo- corneal nurse
- Refraction optometrist
- slit lamp examination research team
- Patient QOL questionnaire

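### The protocol calls the trial blinded without saying who is masked; the role that reads the primary acuity also takes the OCT that can show the graft type, and that acuity is not tied to the scheduled refraction

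*Protocol*

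**What the plan says.** **Blinding.** The Randomisation paragraph (printed under Exclusion criteria) states: "As our study is blinded, a concealment list will be made to produce kit numbers in an agreed format". It does not name the masked parties, and no other section does. Allocation takes place on the day of surgery, and the graft is then prepared according to it (Day of Surgery).

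**Primary endpoint.** It is given as "The improvement in vision measured in LogMAR units at 12 months", and "The time points will be pre-operative, at 6months and then at the last visit in 12months". The protocol does not say whether the acuity is unaided, with the patient's own glasses, or best-corrected.

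**Who measures.** At 4 weeks the schedule lists "vision / IOP / specular / OCT corneal nurse". At 12 months it lists "vision / IOP / specular / pentacam / anterior segment OCT and photo- corneal nurse" and, as a separate item, "Refraction optometrist". The 6-month visit has the same two items. The 10-week and 9-month visits also give vision and OCT to the corneal nurse. At the first clinic visit the entry is "Visual acuity testing performed by staff nurse /HCA", with auto-refraction by the corneal nurse and no optometrist.

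**What the OCT can show.** The background sections give a thickness of 70-130 microns for Microthin DSAEK and 15-20 microns for DMEK. The first secondary endpoint expects the arms to differ by at least 50 microns. The description of tests says that anterior segment OCT gives a cross-section of the cornea and is used to look at the graft.

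**The concern.** Kit numbers mask treatments that look alike. In this trial the operating team necessarily knows which graft it has prepared and implanted, so masking can only apply to the patient and to whoever measures the outcome. The protocol claims blinding, but its visit schedule does nothing to protect the person reading the primary outcome. The same role is assigned the image on which the two grafts differ.

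Acuity testing needs the patient's cooperation and the examiner's judgement, so an examiner who knows the arm could shift the primary endpoint in one direction. Analysis cannot remove such a shift afterwards.

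The second gap concerns what is measured. Vision and refraction are separate, unlinked items, so acuity with any form of correction would satisfy the endpoint as written. If correction varies between patients or visits, the measured improvement mixes refractive error with graft performance. Both matters are settled at the visit itself, so they belong in the protocol and cannot be left to an analysis plan.

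**Working it through.** **Inputs from the protocol** (Statistics and data analysis): 28 eyes per arm, difference 0.1, SD 0.1, two-sided alpha 0.05, equal-variance t-test. Graft thicknesses are from the Microthin DSAEK and DMEK sections.

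**1. The plan's own figure.**
- SE of the difference = 0.1 × √(2/28) = 0.0267 logMAR.
- Noncentrality = 0.1 / 0.0267 = 3.74 on 54 degrees of freedom.
- Exact power = 95.7%. The stated 80% therefore holds as a lower bound, and this point disputes no figure in the plan.

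**2. Can the OCT separate the arms?**
- Smallest gap between the stated ranges: 70 − 20 = 50 microns.
- Largest gap: 130 − 15 = 115 microns.
- The ranges do not overlap, and the smallest gap matches the protocol's hypothesis of at least 50 microns. That the scan can reveal the arm is an inference from these figures; the protocol does not say so outright.

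**3. When is the acuity reader exposed?**
- Vision and OCT fall to the corneal nurse role at 4 weeks, 10 weeks, 6 months, 9 months and 12 months.
- Within each visit vision is listed before OCT. The 12-month reading is therefore exposed mainly through the four earlier scans.

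**4. Smallest significant observed difference.**
- t(0.975, 54) × SE = 2.005 × 0.0267 = 0.054 logMAR, about half the planning difference of 0.1.

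**5. Sensitivity to assessor bias.** The shift is an assumption; the protocol gives neither size nor direction. With no true difference and SD 0.1, the noncentrality is shift / 0.0267.

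| Assumed shift (logMAR) | Chance of a significant result |
|---|---|
| 0 | 5% |
| 0.01 | 6.6% |
| 0.02 | 11.4% |
| 0.03 | 19.7% |
| 0.05 | 45.1% |

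**6. Sensitivity to refractive noise.** The total SD is an assumption; the planned 0.1 may already include some of this noise. The difference stays at 0.1 with 28 per arm.

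| Assumed total SD | Power |
|---|---|
| 0.10 | 95.7% |
| 0.12 | 86.5% |
| 0.13 | 80.7% |
| 0.15 | 68.8% |
| 0.20 | 45.1% |

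Power falls below 80% once the SD exceeds about 0.131.

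**The case against.** The other side has several fair points.

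- **A reader might infer that the assessor knows the arm from 4 weeks on.** The text does not support that. Corneal nurse is a role; nothing says the same individual attends each visit or interprets the scan, and vision is listed ahead of OCT. What stands is that the assessor may know the arm and that nothing in the schedule prevents it.
- **A reader might take it that the operating surgeon opens the envelope.** The protocol says the PI or a delegate does. A surgeon's knowledge of the operation is also compatible with masking others. The difficulty is that the masked parties are not named.
- **A reader might count the nurse who reads acuity as part of the research team.** The consent discussion has a "research team to include Consultant / Corneal fellow and corneal specialist nurse", but the follow-up visits list the corneal nurse and the research team separately. The equation is only an inference, and the point does not need it.
- **A reader might infer that the endpoint is uncorrected vision.** Nothing says so. The optometrist's refraction is scheduled only at 6 and 12 months, which are the two post-operative endpoint times, and this suggests that refracted acuity was intended. What stands is that the link is unstated. The protocol also offers no evidence that the two grafts differ in refractive effect.
- **Baseline acuity precedes allocation.** Weakness in the baseline method affects both arms alike and adds noise, not bias between arms. This is correct and limits the baseline part of the point.
- **The bias figures are illustrative.** They show how sensitive the test is. They do not show that bias occurs.

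**Conclusion.** The point holds in this form: the protocol claims blinding without saying who is masked, leaves the reader of the primary acuity open to unmasking through OCT, and does not tie that acuity to the refraction already scheduled. This goes beyond missing detail, because following the schedule as written creates the exposure and a specific, inexpensive change removes it.

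The size is conditional. The significance threshold of 0.054 logMAR follows from the protocol's own inputs. The rise in the false-positive rate from 5% to about 11-20% rests on an assumed systematic shift of 0.02-0.03 logMAR. The loss of power rests on an assumed SD above 0.1. The documents do not show that either has happened or will happen. The change should be made, but the gap does not invalidate the design.

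**What to change.** 1. **Primary end point and the 6- and 12-month visits.** Define the primary acuity as best spectacle-corrected logMAR, recorded by the optometrist at the refraction already scheduled. Take it before slit lamp and imaging, without access to the OCT, the operation note or the allocation. Using the optometrist protects masking only if these conditions are written down.
2. **Randomisation paragraph.** Replace the general claim of blinding with a statement that the acuity assessor is masked and that surgeons and imaging staff are not. Say explicitly whether the patient is masked, since the protocol is silent on this. Kit numbers may stay as coded identifiers that keep the allocation out of the records.
3. **Pre-operative visit.** No optometrist is listed there. Record logMAR acuity with correction from the auto-refraction already taken. This does not fully match the follow-up method, but because baseline precedes allocation the remaining difference adds noise and not bias between arms.

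**Cost.** Tests are re-ordered within existing visits and notes are withheld from the optometrist, with a slightly longer refraction slot at two visits. No new staff, extra visits or extra patients are needed. Sample size and alpha do not change, so power stays at 95.7% on the protocol's inputs.

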## Serious adverse events – definitions and reporting:

Damaged corneal transplant, primary transplant failure, post-operative endophthalmitis, and any type of serious adverse events will be reported to NHS Blood and Transplant Serious events form. They form the Independent monitor committee for all the graft that are done in UK.

## Statistics and data analysis:

Based on power calculation, we estimate a sample size of 56 would provide sufficient power to the study. Group sample sizes of 28 and 28 achieve atleast 80% power to reject the null hypothesis of equal means when the mean difference of intended primary outcome measure is 0.1 with a standard deviation of 0.1 and with a significance level (alpha) of 0.050 using a two-sided two-sample equal-variance t-test. Only one eye of each patient will be enrolled in the study. An interim data analysis and power calculation will be undertaken at 6 months.

Further statistical analysis will be carried out using parametric and non-parametric tests depending upon the distribution of the results and comparing secondary outcome measures between the two arms of the study. The transplant thickness and relative visual gain would also be assessed using Pearson correlation coefficient. Kaplan-Meier limit analysis would be used to determine the cumulative probability of the transplant survival in the two groups with multi-variate analysis on factors influencing transplant survival.

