## Microthin DSAEK

In Microthin DSAEK the endothelial transplant is prepared from the cadaveric human donor cornea using a mechanised microkeratome with transplant thickness varying between 70-130 microns. The DSAEK endothelial transplant consists of a monolayer of endothelial cells on the descemets membrane with posterior stromal layer. The conventional DSAEK procedure in comparison yields transplant thickness averaging 170microns with a wide variance between 70-250microns with less than optimum visual results. By regulating the corneal donor thickness using a stromal dehydration technique we have shown a reliable way to create an endothelial transplant thickness of 100microns with minimal variance, termed microthin DSAEK. This technique will be compared to DMEK in this trial.

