## DMEK

In this procedure the endothelial transplant is prepared by manual peeling of the descemets membrane, which consists of a monolayer of endothelial cells without the posterior corneal stroma measuring 15-20 microns in thickness.

Both transplants (MT-DSAEK and DMEK) are delivered to the eye using a sterile disposable surgical injecting instrument. And the attachment of the transplant to the host cornea is assisted with an air bubble in the anterior chamber.

There is evidence in the literature on the widespread use of both these techniques and several studies comparing **conventional** DSAEK with DMEK. However, there has not been an attempt in literature to compare **Microthin** DSAEK with DMEK. Also, these trials have been retrospective and not randomised. Our study proposes a randomised controlled comparison of outcomes between Microthin DSAEK and DMEK to identify the effect of variations in corneal transplant preparation techniques in the field of corneal endothelial keratoplasty to visual outcomes.

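### The planned correlation of graft thickness with visual gain does not separate or adjust for arm; over all eyes it would largely restate the arm difference

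*Protocol*

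**What the plan says.** In Statistics and data analysis, directly after a sentence about "comparing secondary outcome measures between the two arms of the study", the Protocol adds: "The transplant thickness and relative visual gain would also be assessed using Pearson correlation coefficient". It does not say whether the coefficient is computed over all eyes, within each arm, or with adjustment for arm.

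The thickness of each graft type is given in the background sections: "transplant thickness varying between 70-130 microns" for Microthin DSAEK and "measuring 15-20 microns in thickness" for DMEK. Secondary end point 1 hypothesises that the two graft types differ by 50 microns or more.

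The sample size paragraph supplies the other inputs. Its effect size reads "when the mean difference of intended primary outcome measure is 0.1 with a standard deviation of 0.1"; it plans 28 eyes per arm, claims power of 80% or more, and uses a t-test, two-sided at the 5% level. The primary end point section states a larger target: "Our hypothesis assumes to detect a 2 line difference in final visual outcomes between the groups".

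**The concern.** A Pearson coefficient relates two variables and has no place for a third. Here one of the two, thickness, is fixed almost entirely by the randomised technique. The lowest Microthin DSAEK value (70) lies 50 microns above the highest DMEK value (20), so a scatter plot of all eyes would show two separate clusters, one per arm. A line through two clusters mainly joins their means, and its slope is the arm difference in vision divided by the arm difference in thickness.

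The techniques differ in more than thickness. By the Protocol's own description, one graft carries posterior stroma and is cut with a microkeratome; the other has no stroma and is peeled by hand. A pooled coefficient cannot say which of these accounts for a difference in vision. If the trial finds a difference between arms, the same data would almost automatically give a significant thickness correlation. A reader could take it for separate evidence that thickness is the mechanism, although it would have tested nothing beyond the arm comparison.

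**Working it through.** **Inputs.** From the Protocol: 28 eyes per arm, difference 0.1, SD 0.1, two-sided alpha 0.05; Microthin DSAEK thickness 70-130 microns, DMEK 15-20 microns. Assumed: thickness uniform over each range (or, for Microthin DSAEK, normal with mean 100 and SD 10, 15 or 20); the stated ranges also describe the thickness that is analysed; one line of acuity equals 0.1 logMAR; alternative outcome SDs of 0.2 and 0.3.

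**1. The plan's own figure.** A two-sided t-test with 28 per arm, difference 0.1 and SD 0.1 has noncentrality (0.1/0.1) × √(28/2) = 3.74 on 54 degrees of freedom. Power is 95.7%, so the claim of at least 80% is true.

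**2. How far thickness is a label for arm.** With uniform thickness:
- Means: 100 and 17.5, a gap of 82.5. Between-arm variance: (82.5/2)² = 1701.6.
- Within-arm variances: 60²/12 = 300 and 5²/12 = 2.08, average 151.0.
- Correlation of thickness with arm: √[1701.6/(1701.6 + 151.0)] = 0.958.

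Simulation gives 0.96 for the uniform case and 0.95-0.99 over the four thickness distributions.

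**3. Expected pooled coefficient with no relation within either technique.** It is the product of two correlations: thickness with arm (0.958), and arm with outcome, d/√(d² + 4), where d is the arm difference divided by the SD. At d = 1 this is 0.958 × 0.447 = 0.43.

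**4. How often the pooled test is significant.** 20,000 simulated trials per setting, visual gain independent of thickness within each arm:

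| Arm difference | SD | Mean size of r | Pooled Pearson p<0.05 | Arm t-test p<0.05 |
|---|---|---|---|---|
| 0 | 0.1 | 0 | 5% | 5% |
| 0.05 | 0.1 | 0.23-0.24 | 41-44% | 45% |
| 0.1 | 0.1 | 0.43-0.44 | 93-95% | 96% |
| 0.2 (two lines) | 0.1 | 0.67-0.70 | 100% | 100% |
| 0.1 | 0.2 | 0.24 | 43% | 46% |
| 0.1 | 0.3 | 0.16 | 22% | 23% |

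Ranges cover the four thickness distributions; the last two rows use the uniform one. At difference 0.1 and SD 0.1 the pooled test and the t-test reach the same decision in 97-99% of trials.

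**5. Can the pooled test tell the two explanations apart?** Suppose instead that thickness explains the whole difference, with a slope of 0.1/82.5 = 0.0012 logMAR per micron within each arm as well as between arms. The pooled test is then significant in 97% of trials, against about 94% when thickness has no effect within a technique. It barely distinguishes the two.

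**6. The alternatives.** At difference 0.1 and SD 0.1 with no within-technique relation, the partial correlation adjusted for arm rejects in 5.1-5.4% of trials and the correlation in Microthin DSAEK eyes alone in 4.8-5.3%. Both hold the nominal 5%.

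**7. What the alternatives cost.** After adjustment for arm, Microthin DSAEK supplies 300/(300 + 2.08) = 99.3% of the usable variation in thickness. The standard error of the slope is about 0.1/√(27 × 302.08) = 0.0011 logMAR per micron, nearly as large as the 0.0012 slope in step 5. Power to detect that slope is about 18-19%.

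**The case against.** The strongest objection is that pooling is inferred. The sentence is silent on arm, and a statistical analysis plan that is not shown could specify the handling. This stands, and the point is worded accordingly: the analysis as named neither separates nor adjusts for arm. It does not remove the point. The Protocol names a specific two-variable method, and the sentence that follows, on Kaplan-Meier analysis, does refer to the two groups and to multivariable analysis, whereas this one does neither.

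A reader might infer that the analysis will declare a thickness effect whatever happens. The documents do not support that. With no arm difference the error rate is 5%, and with a larger SD the rate falls in step with the t-test. Entry acuity runs from 6/9 to perception of light, so an SD of gain above 0.1 is quite possible. Nor does the coefficient purely restate the arm difference: the correlation of thickness with arm is 0.95-0.99, not 1.

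A reader might also infer that, because visual gain contains baseline acuity, the pooled coefficient is driven by who started worst. Allocation is randomised, so baseline is unrelated in expectation to arm, and hence to the thickness gap between arms. It adds noise and pulls the coefficient towards zero. That is a reason to adjust for it, not a source of systematic bias.

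Lastly, the Protocol nowhere says that the coefficient will be read causally. The stated aim concerns technique, which the randomised comparison answers, and this correlation is not a listed end point. When the arms differ, a pooled association is real as a description. This limits the weight of the point, but there is little reason to correlate thickness with vision except to learn about thickness, and the pooled coefficient cannot do that.

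**Conclusion.** The point holds in a conditional form. If the coefficient is computed over all eyes, it largely duplicates the arm comparison and cannot separate thickness from the other differences between the techniques. At the Protocol's design values it would be significant in about 94% of trials with no thickness relation within either technique. The figure is about 43% at an assumed SD of 0.2, 22% at 0.3, and 5% if the arms do not differ.

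This rests on the stated thickness ranges applying to the measurements analysed, and on pooling, which is the natural but unstated reading. The result changes little across the assumed thickness distributions. The primary comparison and the sample size are not touched. It is a cheap improvement to a supplementary analysis.

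**What to change.** Replace the sentence on the Pearson coefficient with:

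> The association of graft thickness with 12-month logMAR acuity will be estimated by linear regression adjusted for treatment arm and pre-operative acuity (or within each arm), with 95% CI; a coefficient pooled over arms without adjustment will not be interpreted as an effect of thickness.

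Using 12-month acuity in place of gain loses nothing if gain means the simple change from baseline: once pre-operative acuity is in the model, the thickness coefficient is the same apart from its sign.

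The cost is one sentence and some precision. The estimate rests mainly on the 28 Microthin DSAEK eyes, whose thickness the Protocol expects to vary little around 100 microns, so the interval will be wide. Less spread than the uniform range assumed above would widen it further. The result should be reported as exploratory.
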